#### **Bias**

Efforts to address potential sources of bias:

**Clear Inclusion and Exclusion Criteria:** The inclusion criteria are clear to select patients that are representative of the target population (patients with gastric adenocarcinoma) and that there is no bias in participant selection.

**Control of Confounding Factors:** There are some confounding factors that may influence the study results, such as age, sex, Weight; Height; Body mass index; **Presence of other diseases:** Diabetes; Arterial Hypertension; Dyslipidaemia; Stroke; Heart attack). This will be achieved through appropriate statistical techniques or data stratification during analysis.

**Uniformity in data records:** There was uniformity in the data recorded for each participant who agreed to be submitted to MGPT, minimizing the variability between records or the missing clinical data.

**Consistent and Accurate Data Collection:** This will be achieved through adequate training of interviewers or data collection personnel and the use of standardized data collection protocols.

**Blind Data Assessment:** After collection, the data will be pseudo-anonymized so that the researcher who analyses the data will not have access to the patient's identifying data.

**Time-Sensitive Analysis:** Data analysis takes into account the timing of data collection relative to relevant clinical events.

**Sensitivity Analysis:** It will be performed a sensitivity analyses to assess the robustness of the results across different results of MGPT and clinical factors.

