## Objectives

The **main objective** of this research is to quantify and characterize the PV found in MGPT of GC patients in Alto Alentejo (Portugal).

The **specific objectives** are:

- Determine the global rate of PVs in GC patients of Alto Alentejo;
- Determine which PVs are most common in our GC population;
- Correlate the PVs found with clinical factors: Age at diagnosis; Sex; Weight; Height; Presence of other diseases (Diabetes; Arterial Hypertension; Dyslipidaemia; Stroke; Heart attack); Date of diagnosis; Stage at diagnosis; Histologic subtype; Surgery for GC; Personal history of other cancers; Familial history of GC and other cancers;
- Correlate the PVs found with prognostic factors: 12-month survival rate; mortality.

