## Methods

### Study design

Observational, retrospective study

Despite this design, there was uniformity in the data recorded for each participant who agreed to be submitted to MGPT, minimizing the variability between records or the missing clinical data.

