### Setting

This study takes place at the Unidade Local de Saúde do Alto Alentejo (ULSAALE). The MGPT was always performed in the same laboratory (Germano de Sousa – Centro de Genética Laboratorial) using peripheral blood samples from patients with GC.

Two types of MGPT were used:

- MGPT 4005 (15 genes): APC, ATM, BLM, BMPR1A, CDH1, CTNNA1, EPCAM, MLH1, MSH2, MSH6, PMS2, PTEN, SMAD4, STK11/TP53.
- MGPT 4013 (30 genes): ATM, BARD1, BLM, BRCA1, BRCA2, BRIP1, CDH1, CHEK2, EPCAM, FANCC, MLH1, MRE11A, MSH2, MSH6, MUTYH,

NBN, NF1, PALB2, PMS2, PTEN, RAD50, RAD51C, RAD51D, RECQL4, RINT1, SLX4, SMARCA4, STK11, TP53, XRCC2.

The majority of patients with GC were tested with MGPT 4005. Patients with neoplasms other than GC or with a family history of other neoplasms were tested with MGPT 4013. The decision to perform MGPT and the choice of panel type were made in multidisciplinary consultation.

The recruitment process takes place between January 2023 and December 2024. All data will be collected and entered in a database until September 2025

The manuscript for publication will be written between October and November 2025.

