### **Participants**

Eligibility criteria:

- Adult patients (over 18 years old) with a histologically proven diagnosis of gastric adenocarcinoma that have done MGPT between 2023 and 2024;
- Ability to understand and speak Portuguese and/or English language;
- Ability to reliably provide informed consent for inclusion in the study.

There are no matched or randomized groups.

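### The Bias section says selection is free of bias, but only tested, consenting patients can enter, so the study estimates the PV rate in that subset and not in all gastric cancer patients of the region

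*Combined protocol and SAP*

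**What the plan says.** The Bias section presents the eligibility criteria as a safeguard. They are said to select patients who represent the target population, defined there as patients with gastric adenocarcinoma, so that "there is no bias in participant selection". The first specific objective in the Objectives section matches that population: "Determine the global rate of PVs in GC patients of Alto Alentejo".

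Other sections describe how a patient comes to be in the sample:

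- **Setting:** "The decision to perform MGPT and the choice of panel type were made in multidisciplinary consultation". No criterion for offering the test is given.
- **Participants:** a patient must have a "histologically proven diagnosis of gastric adenocarcinoma that have done MGPT between 2023 and 2024". A further criterion is "Ability to reliably provide informed consent for inclusion in the study".
- **Study design** (repeated under Bias): the records cover "each participant who agreed to be submitted to MGPT".
- **Data sources:** clinical history and personal data come from a questionnaire given in a personal interview, supplemented by the medical record.

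No section says that every gastric cancer patient was offered MGPT. None plans a count of patients who were not offered it, declined it or did not consent.

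**The concern.** Eligibility criteria act only on patients who reach them. Here the decision to test, and the patient's agreement to it, come before eligibility is assessed, and an untested patient cannot enter at all. Clear criteria cannot undo selection that has already happened.

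This matters because of how the rate will be used. Risks and Benefits says the study may help clarify whether hereditary gastric cancer is more common than the 3-5% in the literature, and that this might justify population screening. If the chance of being tested was related to carrier status, a rate from tested patients could differ from 3-5% for that reason alone. Followed as written, the plan would report the figure as the regional rate, and a reader would have no count with which to judge how far the two might differ.

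**Working it through.** **1. Steps between diagnosis and analysis.** All come from the sections cited above.

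| Step | Who is lost | Does the plan count them? |
|---|---|---|
| Decision to test in consultation | Patients not put forward | No |
| Agreement to MGPT | Patients who decline | No |
| Study consent | Those unable or unwilling | No |
| Interview | Those who cannot be interviewed | No |

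The sample is what remains after these steps. The claim of no selection bias would need each step to be unrelated to carrying a PV, or to lose almost nobody. The documents establish neither.

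**2. The plan's sample size.** Study size gives 56 patients from 65 annual cases (2020), at 95% confidence and a 5% margin. The expected proportion is not stated, so I assume p = 0.5.

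- n0 = 1.96² × 0.5 × 0.5 / 0.05² ≈ 384.15
- n = n0 / (1 + (n0 − 1)/65) = 384.15 / (1 + 383.15/65) = 55.72, rounded up to 56

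The figure reproduces, as a simple random sample from one year's 65 cases. No such random draw is described in Setting or Participants.

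**3. What share of patients the 56 would be.** This is not known. The 56 is a target, not the number tested, and two denominators are arguable:

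- One year's cases, as in Study size: 56/65 = 86%.
- The 24-month window, assuming 65 cases a year: 56/(2 × 65) = 56/130 = 43%.

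Participants dates the test and not the diagnosis, so some tested patients may have been diagnosed before 2023. Neither denominator is shown to be the source population.

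**4. Illustration in both directions.** The documents give no PV rates by testing status, so every rate here is assumed. With rate a in the 56 tested and rate b in the rest:

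rate in all patients = [56a + (N − 56)b] / N

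For example, a = 10%, b = 3%, N = 130 gives (5.60 + 2.22)/130 = 6.0%. With N = 65 it gives (5.60 + 0.27)/65 = 9.0%.

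| Tested (what the study would report) | Untested | All, N = 65 | All, N = 130 |
|---|---|---|---|
| 10% | 3% | 9.0% | 6.0% |
| 5% | 3% | 4.7% | 3.9% |
| 5% | 5% | 5.0% | 5.0% |
| 3% | 5% | 3.3% | 4.1% |
| 3% | 10% | 4.0% | 7.0% |

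The gap depends on the untested share and on the difference in rates. It vanishes if either is zero, and it can have either sign.

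**5. Sampling error, for scale.** An assumed 3 positives in 56 is 5.4%, with an exact 95% interval of 1.1% to 14.9%. The milder shifts in the table are small beside that. The interval, however, describes random error in the tested group and takes no account of who was tested.

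**The case against.** The best defence has five parts.

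- **The consultation may have been routine.** Setting says who decided, not that the decision was restrictive, and the Introduction leans towards testing unselected patients. This stands as a possibility. No section says that testing was universal.
- **Panel use argues against strong enrichment.** The 30-gene panel went to patients with other neoplasms or a family history of them, yet most patients had the 15-gene panel, so most of those tested apparently lacked those features. This is fair evidence against one kind of enrichment. It does not exclude selection on young age, diffuse type or familial gastric cancer. Nor does the sentence about the majority say what share of gastric cancer patients was tested.
- **The sentence states an aim.** It appears under efforts to address bias, and the main objective is already limited to variants found in MGPT. Even as an aim, it relies on criteria that cannot deliver it, and the first specific objective remains unqualified.
- **Enrichment would be partly visible.** Age, stage, histologic subtype and family history are recorded for participants (Table 2). That helps, but there is nothing on untested patients to compare them with.
- **Sensitivity analyses are planned.** Statistical methods allows the inclusion criteria to be varied. This cannot bring back patients who were never tested, and neither can adjustment within the sample.

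A reader might infer that the reported rate will be inflated because consultation favoured high-risk patients, or that only 43% of patients were tested. The documents support neither. They give no offering rule, no number tested and no rates by testing status, and the 43% divides a target derived from 65 cases by an assumed 130.

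**Conclusion.** The claim of no selection bias is wrong as written, because it asserts a property that the described route of entry does not provide. What the design can estimate is the PV rate among tested and consenting gastric cancer patients. Calling it the rate in all gastric cancer patients of Alto Alentejo needs evidence of near-complete testing and participation, or of testing unrelated to carrier status, and the documents offer neither.

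The size and direction of any bias are not known. In the illustration the rate in all patients lies between 4 percentage points below the reported rate (10% against 6.0%) and 4 points above it (3% against 7.0%), both with N = 130. With N = 65 the gap is 1 point at most in the scenarios shown. These figures rest on assumed rates and denominators; they show what is possible, not what is likely.

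The remedy is a correction of wording and reporting. It is worth making because it changes what the study may conclude, including the comparison with 3-5%.

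**What to change.** 1. **Bias section.** Replace the sentence with a statement that the sample is the tested and consenting subset, and that selection into testing is a limitation.
2. **Flow counts.** For 2023-2024, report the numbers of gastric cancer patients diagnosed at the centre, offered MGPT, tested, consented and analysed. Report separately how many tested patients were diagnosed before 2023. If offers were not recorded, say so.
3. **Wording of the rate.** In the first specific objective, the conclusion and the comparison with 3-5% in Risks and Benefits, refer to the PV rate among tested gastric cancer patients, unless the flow counts show near-complete testing.
4. **Any figure for the possible bias.** Mark it as illustrative, show it for N = 65 and N = 130, and include no-difference and reversed scenarios.

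A comparison of tested with untested patients is optional, and only if aggregate hospital counts are available. The protocol cites the National Oncologic Registry for a case count alone, so stage or histology should not be assumed obtainable from it. I would not add a worst-case bound for all diagnosed patients: with 3 of 56 positive and N = 130 it runs from 3/130 = 2.3% to (3 + 74)/130 = 59.2%, which tells the reader nothing useful.

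The cost is a few sentences, one set of aggregate counts (with a check that the ethics approval covers them) and a narrower headline claim. No further patients or tests are needed.

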#### **Study size**

The sample calculation takes into account the number of annual cases of GC recorded in Alto Alentejo (65 cases in 2020, data from National Oncologic Registry). Therefore, the sample calculation suggests that it should include 56 patients with GC, with a confidence level of 95% and a margin of error of 5%.

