#### **Quantitative variables**

For quantitative variables we will do the descriptive statistics analyses with mean, mode, median, standard deviation, interquartile variation, maximum and minimum.

Subgroup analysis will be carried out, for each quantitative and qualitative variable, dividing patients who have positive or negative MGPT. We will analyse the effect measures of the difference between the two groups, with confidence interval (IC) 95%, and if possible, inferential statistical analysis will be conducted.

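### The 5% margin behind the 56 patients appears to rest on treating one year's 65 cases as a closed population; it is not the precision of the global PV rate, for which no interval is planned

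*Combined protocol and SAP*

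**What the plan says.** The Study size section rests on the "number of annual cases of GC recorded in Alto Alentejo (65 cases in 2020", national registry data) and concludes that "it should include 56 patients with GC, with a confidence level of 95% and a margin of error of 5" per cent. It gives no formula, no expected proportion, and no statement of which quantity the margin refers to.

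The first specific objective under Objectives is to "Determine the global rate of PVs in GC patients of Alto Alentejo". Under Setting, "The recruitment process takes place between January 2023 and December 2024". Under Participants, eligible patients are those "that have done MGPT between 2023 and 2024", and a further criterion is "Ability to reliably provide informed consent for inclusion in the study". Setting adds that "The decision to perform MGPT and the choice of panel type were made in multidisciplinary consultation".

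On intervals, the Quantitative variables section says "We will analyse the effect measures of the difference between the two groups, with confidence interval (IC) 95" per cent, where the two groups are MGPT-positive and MGPT-negative patients. Statistical methods again attaches 95% intervals only to differences between those groups. The Bias section asserts that the criteria give a representative sample with no selection bias. Risks and Benefits hopes to help clarify whether hereditary gastric cancer is more frequent than a literature figure of 3–5%.

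**The concern.** A margin of 5 points from only 56 patients is possible at a proportion of 0.5 only if those 56 are most of a closed population. The number 65 in the same section suggests that this is how it was obtained. A finite-population correction is valid for a random sample from a fixed list when inference stops at that list. Here the 65 patients were counted in 2020, the study concerns patients tested in 2023–2024, and nobody is sampled from a list.

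The margin is the only justification given for the study size and the only precision figure in the plan. With no interval planned for the PV rate, a reader may attach ±5 points to the main estimate. If the rate is then set against 3–5%, it could be read as higher than the literature when the data do not show that.

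**Working it through.** **Inputs.** From Study size: N = 65, 95% confidence (z = 1.96), margin d = 0.05, n = 56. Assumed: p = 0.5, because the plan states no proportion; N = 130 for two recruitment years at 65 cases each, with a range of 100 to 160. The plan gives no expected PV rate for these panels, so 3, 6 and 10 positive patients are illustrations.

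**1. Reproducing 56.**

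- n0 = z²·p(1−p)/d² = 1.96² × 0.25/0.0025 = 384.15
- n = n0/(1 + (n0−1)/N) = 384.15/(1 + 383.15/65) = 55.7, rounded up to 56

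Two other routes also give 56: p = 3.8% without correction, and p = 6.8% with N = 130. The section states neither proportion and ties its number to the 65 cases, so the first route is the natural reading. With N = 130 and p = 0.5 the same formula gives 97.3, that is 98 patients.

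**2. Half-width with n = 56 by the same formula.** Half-width = 1.96·√(p(1−p)/56)·√((N−56)/(N−1)), in percentage points:

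| p | N = 65 | N = 130 (N = 100 to 160) | Uncorrected |
|---|---|---|---|
| 0.50 | 4.9 | 9.9 (8.7 to 10.6) | 13.1 |
| 0.05 | 2.1 | 4.3 (3.8 to 4.6) | 5.7 |

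For p = 0.5 and N = 65: 1.96 × √(0.25/56) × √(9/64) = 13.1 × 0.375 = 4.9. The correction therefore supplies the whole gap between 13.1 and 5.

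By this formula, 56 patients exceed a 5-point margin above a rate of 6.8% with N = 130 (9.0% with N = 100, 5.9% with N = 160), and above 3.8% uncorrected.

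**3. Exact intervals.** With few carriers a symmetric normal margin is unsuitable. The uncorrected column is Clopper-Pearson. The finite-population columns keep every carrier count M out of N for which both hypergeometric tails exceed 0.025, with half-width (Mmax − Mmin)/(2N).

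| Positive of 56 | Half-width, N = 65 | Half-width, N = 130 (N = 100 to 160) | Uncorrected 95% interval (half-width) |
|---|---|---|---|
| 3 (5.4%) | 2.3 | 5.0 (4.0 to 5.3) | 1.1–14.9% (6.9) |
| 6 (10.7%) | 3.1 | 6.5 (6.0 to 6.9) | 4.0–21.9% (8.9) |
| 10 (17.9%) | 3.1 | 7.7 (7.0 to 8.4) | 8.9–30.4% (10.7) |

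With 3 positives the uncorrected interval contains the whole of 3–5% and reaches 9.5 points above the estimate (14.9 − 5.4). With 6 it still overlaps 3–5%.

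**4. Does the correction fit the design?** The 65 come from 2020 and eligibility from 2023–2024, so the counted patients are not the study population. Entry depends on a clinical decision to test and on consent, so the 56 are not a random sample of any list.

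**5. Is an interval for the rate planned elsewhere?** Quantitative variables and Statistical methods are the only sections that plan intervals, and both restrict them to between-group differences.

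**The case against.** The arithmetic behind 56 is not wrong, and the closed-population reading is inferred: the section names neither the formula nor the proportion, and 3.8% uncorrected would also give 56. This stands as a caution. It does not rescue the margin: at 3.8% about two carriers are expected among 56 (0.038 × 56 = 2.1), and the exact interval for 2 of 56 is 0.4–12.3%.

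Gastric cancer patients of one region are a bounded population, so some finite-population correction could be defended for a purely descriptive rate. That would argue for a two-year count, not for 65, and it still requires something like random sampling. The sampling objection also weakens any interval as a statement about all regional patients, Clopper-Pearson included; this is why the fix limits the rate to tested, consenting patients.

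The strongest point concerns size. At a 5% rate with N = 130 the formula margin is 4.3 points, within the stated 5, and the large contrasts arise at p = 0.5, which no section suggests as a PV rate. This stands: near 5% the exact interval is wide because n is small, not mainly because the population was miscounted. At higher rates the population matters more.

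Finally, the comparison with 3–5% is an expected benefit, not a listed objective, and hereditary gastric cancer may not be the same quantity as the panel PV rate. That limits how much weight the comparison should carry, but the first specific objective needs an interval regardless.

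**Conclusion.** The concern holds and should be fixed. From the inputs the plan names, 56 patients with a 5% margin follows with p = 0.5 and a correction to N = 65, and that correction does not fit a study of patients selected for testing over 2023–2024. The stated 5% is not the precision of the global PV rate, and no interval for that rate is planned.

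At p = 0.5 the half-width moves from 4.9 to 9.9 points with N = 130, or 13.1 uncorrected. Around a 5% rate the effect of N = 130 is small (4.3 points by the formula), and the practical issue is the small sample. The conclusion rests on p = 0.5 being inferred, on N = 130 being assumed, and on illustrative carrier counts. That no interval is planned rests on none of these.

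**What to change.** - **Study size.** Delete the N = 65 calculation and the 5% margin. If the investigators confirm that 56 is the number they expect, write: *The study size is set by feasibility: 56 tested and consenting patients are expected to be available for 2023–2024. With 56 patients the exact (Clopper-Pearson) 95% CI for the global PV rate would be 1.1–14.9% with 3 positive patients and 4.0–21.9% with 6.* If the expected number differs, recompute both intervals.
- **Statistical methods.** Add: *The global PV rate will be reported with a Clopper-Pearson 95% CI and applies to patients selected for, and consenting to, MGPT.* A Wilson interval would also serve (1.8–14.6% for 3 of 56); what matters is that one method is named in advance.
- **Bias.** Replace the sentence claiming that the inclusion criteria ensure a representative, unbiased sample with: *Participants were selected for MGPT by multidisciplinary decision and consented to inclusion, so the global PV rate may not represent all GC patients of Alto Alentejo.*

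The cost is three short text edits and one added interval, with no extra patients or data. The stated precision becomes less favourable, and the plan must say openly that its size rests on feasibility.

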#### **Quantitative variables**

For quantitative variables we will do the descriptive statistics analyses with mean, mode, median, standard deviation, interquartile variation, maximum and minimum.

Subgroup analysis will be carried out, for each quantitative and qualitative variable, dividing patients who have positive or negative MGPT. We will analyse the effect measures of the difference between the two groups, with confidence interval (IC) 95%, and if possible, inferential statistical analysis will be conducted.

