#### **Statistical methods**

- a) Statistical analysis will be carried out using SPSS software.
- b) In inferential statistical analysis, the normality of the distribution of quantitative variables will be determined by the Kolmogorov-Smirnov test. For variables with normal distribution, the T-sudent test will be used and for those that do not have normal distribution, the Mann-Whitney test will be performed, with the purpose of analysing the statistical significance of the difference between the groups with IC 95% (positive MGPT and negative MGPT). For qualitative variables, the statistical significance of the difference between groups, with 95% CI, will be calculated using the Chi-square test (if more than 10% of the cells in the 2x2 tables have frequencies  $\leq 5$ ) or the Exact Fisher Test.

We will later perform a multivariate analysis with logistic regression to control confounding variables.

- c) Missing data: We addressed missing data by employing multiple strategies. Firstly, we conducted a thorough examination of patterns of missingness to discern if they followed a missing completely at random, missing at random, or missing not at random pattern. Subsequently, for cases with missing data, we utilized multiple imputation techniques to impute missing values based on observed data and variables that were predictive of missingness. Additionally, we performed sensitivity analyses to assess the robustness of our findings to different assumptions regarding the missing data mechanism. Overall, these

approaches allowed us to minimize bias and maintain the integrity of our analyses in the presence of missing data.

d) To conduct sensitivity analysis for this study, we will systematically vary key parameters or assumptions within our analytical framework to assess their impact on the study outcomes. This may involve testing different statistical models, criteria for participant inclusion/exclusion, handling of missing data, or adjustments for potential confounding variables. By exploring a range of scenarios, we aim to evaluate the robustness of our findings and assess the degree to which they are influenced by specific methodological choices or assumptions. Sensitivity analysis allows us to identify the potential sources of uncertainty and to provide a more comprehensive understanding of the reliability and generalizability of our study results.

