**Table 2 - Variables / Measurements**

Type of Variable	Name of Variable	Measurements
MGPT Outcomes variables	MGPT	positive (1) or negative (0)
	PV	integer number
	Likely pathogenic variables (LP)	integer number
	Name of genes with PV	descriptive
	PV in each gene	integer number
	VUS	integer number
Potential confounders variables	Age at diagnosis	Years
	Sex	Female(1)/Male(0)
	Weight	Kg
	Height	cm
	Body mass index	Kg/m 

	Presence of other diseases: Diabetes; Arterial Hypertension; Dyslipidaemia; Stroke; Heart attack);	Yes(1)/No(0) for each disease
	Stage at diagnosis (AJCC staging system);	0, I, IIa, IIb, III, IVa, IVb
	Histologic subtype;	Intestinal (1); Diffuse (2); Mixed (3)
"Exposures" variables	Personal history of other cancers	Yes (1)/No (0)
	Types of other cancer in GC patient	descriptive
	Familial history of GC	Yes (1)/No (0)
	Age of onset of each familial case of GC	integer number
	Familial history of other cancers (specifying)	descriptive
	Age of onset of each familial case of other cancers	Years
Prognostic related variables	12-months survival	Yes (1)/No(0)
	Death due to GC	Yes (1)/No(0)
	Date of death	mm/yyyy
Other variables:	Date of diagnosis	mm/yyyy
	Localization of tumor	Cardia / Fundos / Body / Antrum/pyloro
	Time since diagnosis until the current moment	months
	Surgery for GC	Yes (1)/No (0);
	Type of surgery	Total gastrectomy (1); Subtotal gastrectomy (0)
	Date of Surgery	mm/yyyy
	Histologic staging after surgery	0, I, IIa, IIb, III, IVa, IVb
	Underwent chemotherapy	Yes (1) / No (0)
	Type of chemotherapy	descriptive

	Cycles of chemotherapy	integer number
	Positive MGPT is considered when it is found at least one PV in one gene of teste	A comparative analysis will be made between the individual characteristics and tumor characteristics of positive MGPT cases with those with negative MGPT.

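### Between 18 and about 27 positive-versus-negative comparisons are assessed for significance with no multiplicity control, hierarchy or exploratory label; they should be declared hypothesis-generating

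*Combined protocol and SAP*

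**What the plan says.** The main objective is descriptive: to quantify and characterise the PVs. The first specific objective is the global PV rate. Two further specific objectives are associational: "Correlate the PVs found with clinical factors", followed by a list, and "Correlate the PVs found with prognostic factors: 12-month survival rate; mortality".

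The section Quantitative variables widens the scope: "Subgroup analysis will be carried out, for each quantitative and qualitative variable, dividing patients who have positive or negative MGPT". It then promises effect measures with 95% confidence intervals and adds that "if possible, inferential statistical analysis will be conducted", without saying what would make it possible. The last row of Table 2 describes the same contrast: "A comparative analysis will be made between the individual characteristics and tumor characteristics of positive MGPT cases with those with negative MGPT".

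Statistical methods (b) assigns a t, Mann-Whitney, Chi-square or Fisher test to each type of variable, "with the purpose of analysing the statistical significance of the difference between the groups with IC 95" per cent, and then adds logistic regression. Statistical methods (d) foresees possible variation of models, inclusion criteria, missing-data handling and adjustment.

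The combined protocol and SAP contains no multiplicity adjustment, no ordering of these comparisons and no statement that they are exploratory.

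**The concern.** When many comparisons are each judged at a conventional level and none is marked as exploratory, a reader will take any that crosses the threshold as a finding. The sample size was set for estimating one proportion, not for comparing carriers with non-carriers, and the carrier group is likely to be very small. Power for real differences is then low, while the opportunity for a chance result grows with each variable added.

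The PV rate itself is not affected. What is at stake is how the two associational objectives may be read, and whether the report can present a nominally significant clinical or prognostic correlate as established.

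**Working it through.** **1. The plan's own figure.** Study size gives 56 patients from 65 annual cases, 95% confidence and a 5% margin. Assuming p = 0.5, n0 = 1.96² × 0.25 / 0.05² = 384.1. With the finite-population correction, 384.1 / (1 + 383.1/65) = 55.7, rounded up to 56. The figure is reproduced, and it is a size for one proportion.

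**2. Carriers.** Risks and Benefits cites a 3-5% prevalence of hereditary gastric cancer. 56 × 0.03 = 1.7 and 56 × 0.05 = 2.8, so 2 to 3 carriers. Panels of 15 or 30 genes might find more, so 6 and 11 carriers (about 10% and 20% of 56) are added as assumptions.

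**3. Number of comparisons.**
- Objectives: age, sex, weight, height, five diseases, date of diagnosis, stage, histology, surgery, personal history of cancer, family history of gastric cancer and family history of other cancers make 16. 12-month survival and mortality bring the total to 18.
- Table 2: 31 non-MGPT variables with each disease counted. Dropping two free-text types (other cancer, chemotherapy), date of death and one of the two duplicate time-of-diagnosis variables leaves 27. This is a count made for this review; the plan gives no total.

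**4. Benchmark.** For k independent tests at exactly 5%, the chance of at least one false positive is 1 − 0.95^k.
- k = 18: 1 − 0.95^18 = 60.3%; expected false positives 18 × 0.05 = 0.9.
- k = 27: 1 − 0.95^27 = 75.0%; expected false positives 27 × 0.05 = 1.35.

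**5. Allowing for small groups.** Tests on discrete data with few carriers often fall short of 5%, so a null simulation was run: n = 56, 1,000 runs per setting, t-tests for continuous variables, and either Fisher/exact or uncorrected Chi-square tests for categorical ones. Yes/no prevalences were assumed between 8% and 70%. Each cell shows the chance of at least one p < 0.05, with the mean number of such results in brackets.

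| Comparisons | Carriers | Fisher/exact | Chi-square |
|---|---|---|---|
| 18 | 2 | 24.5% (0.29) | 49.6% (0.69) |
| 18 | 3 | 34.9% (0.42) | 58.7% (0.84) |
| 18 | 6 | 42.1% (0.54) | 56.6% (0.80) |
| 18 | 11 | 52.6% (0.74) | 62.1% (0.95) |
| 27 | 2 | 44.1% (0.57) | 66.7% (1.06) |
| 27 | 3 | 53.5% (0.81) | 69.2% (1.28) |
| 27 | 6 | 62.7% (0.98) | 71.8% (1.28) |
| 27 | 11 | 68.8% (1.14) | 75.2% (1.36) |

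Mann-Whitney in place of the t-test, with Fisher and 2 to 3 carriers, gives 22.6-33.2% (18) and 39.5-52.8% (27).

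**6. Which column applies.** As worded, Statistical methods (b) sends a 2x2 table to Chi-square when more than 10% of its cells are 5 or below. With 11 or fewer carriers, at least one of the two carrier cells is always 5 or below, which is at least 1 cell in 4, or 25%. Read literally, the rule selects Chi-square for every 2x2 table in these scenarios. Both columns are shown in case the opposite was meant.

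**7. What a formal adjustment would do.** Holm's first threshold is 0.05/18 = 0.0028 or 0.05/27 = 0.0019. With 2 carriers among 56 there are 56 × 55 / 2 = 1,540 possible carrier pairs. For a yes/no variable, Fisher gives 3/1540 = 0.0019 if both carriers share a level held by only 3 patients, and 6/1540 = 0.0039 if 4 patients hold it. So even the 18-test threshold is reached only when both carriers share a level held by at most 3 patients.

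**The case against.** The strongest reply is that the study is descriptive, already promises effects with 95% intervals, makes testing conditional and nowhere writes a 5% level. All of that is true, and it lowers the severity. It does not remove the point. The correlations are declared specific objectives, statistical significance is the stated purpose of the tests, and a condition without a criterion leaves the choice of what to test until the data are seen.

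The count of 27 is soft. Several variables exist only in subsets (type and date of surgery, chemotherapy cycles, relatives' ages at onset), and the closing row of Table 2 arguably leaves treatment variables out. The simulation treated these as complete and modelled only the weight-height-BMI link. Other links, such as that between 12-month survival and death, would generally lower the figures. The variations in Statistical methods (d) are optional re-examinations of the same comparisons, so they are not counted as new hypotheses.

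Three stronger readings are tempting and are not supported:
- A reader might infer that a reported significant correlate is probably false. The calculation gives the chance of any false positive when nothing is associated. The share of significant results that are false also needs power and prior plausibility, which were not computed. The complete null is itself doubtful: the Introduction ties *CDH1* to early-onset diffuse disease, and Setting makes panel size depend on personal and family cancer history.
- A reader might infer that a chance correlate would be used to decide who is tested. Risks and Benefits says that no additional intervention will be proposed, and its remark on screening concerns prevalence.
- A reader might infer that a formal adjustment is required. With 2 to 3 carriers it would leave almost no power, so it is a matter of choice.

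**Conclusion.** The point holds, at moderate weight. The plan sets up 18 comparisons in the Objectives, and up to about 27 through Table 2, for assessment at an implied two-sided 5% level where testing is possible. It does not say that they are exploratory. If nothing is associated, at least one nominally significant result has a chance of about 25% to 75%. At the 2 to 3 carriers implied by the cited prevalence, it is 25-35% (18 tests) or 44-54% (27 tests) with Fisher, and 50-59% or 67-69% with Chi-square as the rule is worded. Describing this as roughly an even chance would pick one point from a wide range.

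These figures rest on assumed variable prevalences, near-independence and complete data; correlated variables lower them. The lowest scenarios are still between four and five times a nominal 5%. The descriptive PV rate is untouched.

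**What to change.** In Objectives and Quantitative variables, state that the global PV rate is the primary result. State also that all positive-versus-negative comparisons, including the logistic models and the variations under Statistical methods (d), are exploratory and hypothesis-generating.

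In Statistical methods (b), replace the significance purpose with wording such as: *All planned comparisons will be reported as effect estimates with 95% confidence intervals and unadjusted p-values, together with the number of comparisons made. No association will be described as established on the basis of these analyses.* A comparison that cannot be estimated should be listed as such, so that the feasibility condition does not become a silent selection.

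A multiplicity-adjusted p-value is optional. If used, choose one method in advance: Holm limits the chance of any false positive, whereas Benjamini-Hochberg limits the false discovery rate, so they are not interchangeable.

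The cost is a few sentences of plan text, with no new data. The downside is that no clinical or prognostic correlate can be claimed as confirmed.
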